Length of follow-up for each patient: 6 months

Expected end-date of study: January 31st, 2020

XII. STUDY DESIGN/METHODOLOGY

This will be a single institution, prospective, single-blinded, randomized, controlled effectiveness study with 2-armed parallel-group sequential design to assess the efficacy of intraoperative intercostal nerve cryoablation in postoperative pain control when compared to our current standard care, local anesthesia infiltration of Exparel®.

Screened patients meeting the eligibility criteria will be randomized into one of the two study groups. Both patient groups will receive intraoperative local analgesia infiltration with Exparel® prior to wound closure and patient-controlled analgesia (PCA) postoperatively. Each patient will choose whether or not they will use PCA. The first group (A) of patients will receive intraoperative intercostal nerve cryoablation using CryoICE® CRYO2 cryoablation probes (AtriCure, Inc) to intercostal spaces 4th to 10th in thoracoabdominal aortic repairs and 4th to 8th in descending thoracic aortic repair cases prior to wound closure. This procedure will be performed under electromyography to confirm the successful ablation of the nerve. The second group (B) of patients will be injected with Exparel® in the surgical wound. We will obtain intraoperative electromyography to evaluate as the control.

On the screening visit, patients should present prior to surgery to receive training on the NPS and BPI and to be assessed on their preoperative baseline pain level, using BPI. This may be performed prior to surgery in the preoperative holding area, on the inpatient ward, or in the outpatient settings of the McGovern Medical School at UTHealth.

Patients from both groups will receive the same volume of diluted Exparel®, which will be given in four 20ml syringes using 22-gauge needles (266mg of liposomal bupivacaine, equivalent of one 1.3% 20ml vial of EXPAREL, diluted in 50ml of preservative-free normal (0.9%) sterile saline for a total volume of 70ml). Intercostal muscle electromyogram will be performed in both groups. Group A will have it done before and after the cryoablation. This assessment is to confirm the completeness of the intercostal nerve cryoablation, as the waveform of the electromyogram is expected to disappear after an adequate cryoablation. Group B will have the electromyogram prior to wound closure. The surgical wound length will

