7am (+/- 2 hours) of the third to fifth post-op day and as well as on their 30th and 180th post-operative days. After the 180-day follow-up and BPI reporting, the patient terminates his/her enrollment. This enrollment termination does not mean severance of the physician-patient relationship. Patients will be consented and their medical records pertinent to the study will be collected on a case report form and this information will be kept on a secured HIPAA-compliant web-accessed database. No protected health information (PHI) will be maintained on the web-accessible database.

Study Conduct

1. Screening

The research group will assess patients as possible candidates for enrollment based on the inclusion criteria and the planned surgical exposure: median sternotomy, thoracotomy, midline laparotomy, and/or thoracoabdominal incision. Once the eligibility is met, an informed written consent will be collected. A member of the research team - the PI, Co-PI, research coordinator, or nurse will obtain the consent from the surgical candidates who met the preliminary inclusion criteria. The consent process will take place either during the preoperative clinic visit, upon inpatient admission, or in the preoperative holding area. Patients will be consented before their surgical procedures and will be given the appropriate time to think and discuss with family about being part of the study. There will also be given enough time for the patients to ask questions about the protocol and research study. A copy of the signed informed consent shall be provided to the patient, a copy will be placed in the patient's hospital chart, and a copy will be kept by the research team. Medical/surgical history, vital signs measurements, drug/alcohol screening, and standard preoperative testing will also be performed as per the usual surgical practice.

2. Quality of life assessment - Brief Pain Inventory

The impact of pain on patient's quality of life will be assessed through a brief pain inventory (BPI) that should be done before surgery, at 7am (+- 2 hours) of the third to fifth post-operative day as well as on their 30th and 180th post-operative days. The BPI

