will be presented in an easy to comprehend questionnaire for the patients to quantify and communicate their pain experience and how it is affecting their life. It is designed such that patients with 6th-grade education should be able to complete the questionnaire on their own. Question and answers will be provided in a check-box format. The BPI that will be used on this study will be the short version. Patients with difficulty reading or who are physically unable to complete the questionnaire will be assisted by the research team based on their verbal responses to the BPI questions.

4. Enrollment

After the screening is done, the eligibility criteria are met, and the patient is consented; the patient will be enrolled in the trial. At this point, the study coordinator/research office will be notified so that the patient can be randomly allocated to one of the study groups.

5. Randomization and Allocation Concealment

Randomization and allocation concealment will be performed via a web-based/computer generated block randomization sequence/list secured in a password-protected secure computer in the trial office accessible only to the research staff independent of the trial administration process, who are not involved in the recruitment, data collection, analysis, assessment and/or follow-up. This office/research staff will be contacted by the blinded research assistant/investigator to provide certain specific

6. Preoperative assessment

Pain assessment will be also done using the BPI form.

7. Follow-up

After the surgical procedure is done, the follow-up will be:

- i. 7am (+ or - 2 hours) of the third post-op day: the NPS and the the BPI and 5 -point scale analgesia satisfaction survey will be assessed
- ii. 7pm (+ or - 2 hours) of the third post-op day: the NPS will be assessed
- iii. 7am (+ or - 2 hours) of the fourth post-op day: the NPS and the the BPI and 5 -point scale analgesia satisfaction survey will be assessed
- iv. 7pm (+ or - 2 hours) of the third post-op day: the NPS will be assessed

- v. 7am (+ or - 2 hours) of the fifth post-op day: the NPS and the the BPI and 5-point scale analgesia satisfaction survey will be assessed
- vi. 7pm (+ or - 2 hours) of the fifth post-op day: the NPS will be assessed
- vii. 30 days after the procedure, the BPI and 5-point scale analgesia satisfaction survey will be assessed.
- xiii. Final visit, 180 days after procedure, the BPI and 5-point scale analgesia satisfaction survey will be performed.

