8. Termination of enrollment

Patient will be considered to have his/her enrollment terminated:

- i. After the 180-day follow-up visit, or
- ii. If follow-up is lost after several attempts to contact patient, or
- iii. If any medical/surgical/environmental condition develops that would affect or impair primary or secondary outcomes measurements results, or
- iv. If the study is terminated, or
- v. If the patient dies.

9. Termination of Study

- i. End of study period
- ii. If a clinically/statistically significant difference is achieved early during an interim analysis.

XIII. ADVERSE EVENT REPORTING

Patients enrolled in the trial will be informed to report any unwanted effect at any time during the study. Adverse effects of intercostal nerve cryoablation will be made plain to the patients during the screening/enrollment as well as in the informed consent process. Most adverse side effects are injury of the lung or other surrounding organs/tissues, which may happen if cryoablation probe is misplaced to the organ/tissue. This is extremely rare amongst trained and board-certified vascular surgeons. All the surgeons involved in our study have been extensively trained on the cryoablation technique required for appropriate use. Other adverse effects include

allodynia like-pain after the degeneration of the affected nerve is reported after cryoablation of the nerve, but this is often associated with thoracotomy procedure and not specific to the cryoablation. Safety monitoring will include assessment of:

- i. Adverse Effects (AE)
- ii. Vital Signs
- iii. Wound healing status
- iv. Scarring
- v. Cardiac monitoring

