All items above will be closely monitored in a continuous manner, as part of our standard postoperative care. Any abnormalities found will be promptly assessed and described in the patient's medical records. Once the patient is discharged it is very unlikely that any of the study drugs or procedure will cause any abnormalities. Despite this fact, patients will be asked to contact the hospital in case they feel anything unusual. Definitions and examples of the standard or known adverse events associated with cryoablation is tingling, burning sensation, etc., will be presented to the patient for reference. Patients will be also assessed on the above items on their postoperative clinic visits. In addition, emergency contact information of the office in order to speak to someone regarding documentation of these adverse events will be provided. If need be, an immediate unscheduled visit shall be arranged if the patient so desires. The PI will review AE as they occur, changes to the study design or drug use will be determined on an ongoing basis.

XIV. STATISTICAL ANALYSIS PLAN

A. Primary Outcomes

NPS measures will be plotted for each subject over the initial third to fifth postoperatively and the area under the curve (AUC) integrated to produce a cumulative numeric pain score. The primary endpoint will be measured by a statistical comparison of AUC between the groups, using a Wilcoxon rank-sum test. Randomization is expected to balance the groups with respect to preoperative risk factors.

B. Secondary Outcomes

Cumulative dose of opioid medication will be assessed as the sum of morphine doses dispensed by PCA pump during the admission. In addition, we will evaluate the amount of opioid usage using morphine milligram equivalences.²² This will be compared by unpaired t test. We will also evaluate for the opioid prescription need at the time of discharge, and will be compared by chi-square test. Length of hospital stay will be transformed to log scale to normalize the distribution if necessary and will be compared between groups by an appropriate unpaired statistic. Attainment of physical therapy goal that justifies discharge from inpatient physical therapy within 72 hours will be assessed by an appropriate contingency table test.

C. Sample Size Determination

This is a pilot study to prove the feasibility of intercostal nerve cryoablation in patients undergoing the descending/thoracoabdominal aortic aneurysm repair with thoracoabdominal incision.

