There is a small increased risk to the patients by participating in the study in addition to a possible chance of breach in patient confidentiality as the study involves evaluation of an FDA-approved device. As detailed in the informed consent, the subjects are at risk of developing adverse effects from cryoablation, abdominal muscle bulging or sympathetic nerve paresis. Patients will be offered standard optimal medical therapy options, even if that will culminate in withdrawal from the study. In addition, there is risk of an unintentional disclosure of personal health information.

Benefits to participants

The patients stand to receive no direct benefit from the study. However, in the event our results endorse the published reports of reduction in postoperative pain by cryoablation, the group of patients receiving it might be indirectly benefitted through participation.

XVI. STUDY TIMELINE

Considering our group's monthly average for the given procedures and the enrollment rates, drop-outs and withdrawal, and interim analyses we estimate recruitment of our sample size will take 6 months. Once the follow-up of all enrolled participants is finished, data will be analyzed and published. The following is a chronological estimate of the stages:

Stage 1: Patient screening and enrollment 0 - 6 months

Stage 2: Follow-up up to 180 days from the last patient enrolled (0 – 12 months)

Stage 3: Data collection and analysis 1 month

Stage 4: Presentation and publication period (at the end of data analysis)

XVII. QUALITY CONTROL AND ASSURANCE

The PI will be responsible for monitoring the progress and safety of this pilot trial. Any serious or unanticipated events will be reported in a timely manner to the CPHS.

XVIII. CONFLICT OF INTEREST

There is no relationship between the principal investigator or any other research staff member and AtriCure Inc. The 10 probes are provided from the AtriCure Inc. for the current study.

XIX. FUTURE PUBLICATION AND PRESENTATION

The results of this study will be analyzed and published after the approval of the principal investigator and biostatistician in a peer-reviewed scientific journal and/or presented at an international/national scientific conference or meeting regardless of outcome. The publication will acknowledge members of the study research group for their contributions and will maintain patient data protection.

XX. REFERENCES

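### XII.8.iii can end enrollment for reasons tied to the outcomes, when after surgery no randomised treatment is left to stop and only data are lost

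*Combined protocol and SAP*

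**What the plan says.** **The exit rule.** XII.8 lists the events that terminate enrollment. Item iii is: "If any medical/surgical/environmental condition develops that would affect or impair primary or secondary outcomes measurements results". Loss to follow-up and death are separate items, so item iii reaches patients who are alive and can be contacted. It names no decision-maker and no threshold.

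**Treatment.** XII states: "Both patient groups will receive intraoperative local analgesia infiltration with Exparel® prior to wound closure and patient-controlled analgesia (PCA) postoperatively". Group A also has cryoablation "to intercostal spaces 4th to 10th in thoracoabdominal aortic repairs and 4th to 8th in descending thoracic aortic repair cases prior to wound closure". PCA follows the hospital's standard regimen. The care team may change it for clinical need without a deviation, and it is switched to an oral analgesic on day 3. Under IX, a non-opioid analgesic in the first three days is a deviation, not a ground for withdrawal.

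**Care.** XV.C states: "Patients will be offered standard optimal medical therapy options, even if that will culminate in withdrawal from the study". XII says of the end of enrollment at day 180: "This enrollment termination does not mean severance of the physician-patient relationship". XIII says of the safety items: "Patients will be also assessed on the above items on their postoperative clinic visits".

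**Assessments.** VII and XII.7 schedule NPS twice daily, and BPI and satisfaction once daily, on days 3 to 5. After that, "30 days after the procedure, the BPI and 5-point scale analgesia satisfaction survey will be assessed", and the same two instruments are repeated at day 180. VII lists BPI and satisfaction, including days 30 and 180, under the primary outcome measures.

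**Analysis.** XIV.A states: "The primary endpoint will be measured by a statistical comparison of AUC between the groups, using a Wilcoxon rank-sum test". The visible plan gives no analysis set, no missing-data rule and no provision for collecting data after termination.

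**The concern.** Item iii makes leaving the study depend on something that happens after randomisation and is defined by its effect on the outcomes. The outcomes in VI to VIII are pain, satisfaction, opioid use, physical therapy, length of stay and cost. Many serious complications of aortic repair would affect at least one of these. The background section itself links poor pain control to events such as pneumonia and poor wound healing, and XV.C names muscle bulging and nerve paresis as cryoablation risks. Patients could therefore leave for reasons related to pain or to the procedure, and not equally by arm. The surgical team knows the allocation from wound closure onward.

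If that happens, randomisation no longer protects the comparison of those who remain. What is mainly at stake is the set of scheduled, comparable patient-reported scores. The late ones bear on the duration part of the primary objective. V.I. and VI make clear that a larger trial would follow if this 20-patient pilot shows efficacy, so selective loss could carry into that decision.

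**Working it through.** **1. What does a postoperative exit stop?**

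| Element | When given | Stopped by an exit after surgery? |
|---|---|---|
| Cryoablation (group A) | Once, before wound closure | No, already complete |
| Exparel (both arms) | Once, before wound closure | No, already complete |
| PCA (both arms) | Until day 3, hospital standard | Need not be; not randomised |
| NPS, BPI, satisfaction | Days 3 to 5, 30, 180 | Yes |
| Opioid use, physical therapy, stay, cost | Hospital records | Study collection possibly; the records remain |

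PCA appears under the study-drugs heading (X), but it is the same standard care in both arms.

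**2. Scheduled scores lost, by time of exit.** The counts come from VII and XII.7. Item iv of XII.7 repeats the third day and is read here as the fourth.

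- NPS: 3 days × 2 = 6
- BPI: 3 + 2 = 5 (the preoperative BPI is not counted)
- Satisfaction: 3 + 2 = 5
- Total: 16

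| Exit | NPS lost | BPI lost | Satisfaction lost | Total lost |
|---|---|---|---|---|
| Before day 3 | 6 | 5 | 5 | 16 |
| After day 3 | 4 | 4 | 4 | 12 |
| After day 4 | 2 | 3 | 3 | 8 |
| After day 5 | 0 | 2 | 2 | 4 |
| After day 30 | 0 | 1 | 1 | 2 |

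The unscheduled NPS readings in XII (after extubation and before first rescue) are not counted.

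**3. Range without a distribution assumption.** Assume 10 patients per arm (20 in total; the split is not stated). If k of 10 scores are missing, the arm's mean is undetermined by k × (scale range)/10.

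- 0–10 BPI item: k × 10/10 = 1.0, 2.0, 3.0 points for k = 1, 2, 3
- 1–5 satisfaction scale: k × 4/10 = 0.4, 0.8, 1.2 points

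The widths add across arms. Two exits in one arm, or one in each, leave a between-arm difference on a 0–10 item undetermined by 2.0 points. XIV.C plans for a fall of about two points per day over three postoperative days. That comparison is like for like only for exits early enough to lose those days; no effect is planned for day 30 or day 180.

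**4. Illustration of early, score-related exits.** The plan's figure is 20 subjects, 80% power and alpha 0.05 for a fall from 21 to 14 on the cumulative three-day BPI. No SD is given, so the figure cannot be reproduced independently. Solving backwards for a two-sided 5% t test with 10 per arm gives a standardised effect of 1.325, hence SD = 7/1.325 = 5.28.

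The expected three largest of 10 standard normal values are 1.539, 1.001 and 0.656. If the top scorers of one arm leave before day 3, the mean of the rest shifts as follows:

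- One gone: −1.539/9 = −0.17 SD; × 5.28 = −0.9 points (13% of 7)
- Two gone: −2.540/8 = −0.32 SD; × 5.28 = −1.7 points (24%)
- Three gone: −3.196/7 = −0.46 SD; × 5.28 = −2.4 points (34%)

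The shift favours whichever arm lost the patients. With no true difference, simulated two-sided exact Wilcoxon rejection rates on normal scores are about 4% with no exits, and about 6–7%, 10% and 15–16% with the top one, two or three of one arm gone.

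**The case against.** **Item iii may be meant narrowly.** It can be read as covering patients who cannot give a valid self-report. That would match the eligibility criteria in IX on intubation beyond 48 hours and on difficulty communicating pain. For such patients, continued assessment recovers little while the condition lasts. This is a fair reading, but the text does not confine itself to it: it covers any condition affecting primary or secondary results, and termination also forfeits later assessments that a recovered patient could complete.

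**XV.C is a patient protection.** A reader might infer from it that receiving standard therapy removes the patient. The documents do not support this. The sentence allows for withdrawal and does not order it, and the likeliest added pain treatments are handled elsewhere: PCA changes are not deviations, and early non-opioid analgesics are deviations only.

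**Harms would still be seen.** A reader might infer that terminated patients' harms disappear. Routine monitoring and clinic visits under XIII would still record them, so this does not follow.

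**No bias is demonstrated.** This stands. The shifts rest on a back-solved SD and on an assumed 1 to 3 exits of the highest scorers before day 3, a mechanism the clause does not state. They concern the cumulative BPI, not the NPS AUC, and exits after day 5 leave the scheduled NPS untouched.

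**The plan may say more out of sight.** The second withdrawal criterion in IX breaks off, and the consent form is not available. Either could qualify the rule.

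**Conclusion.** The point holds for exits after surgery under XII.8.iii. As written, the rule discards post-randomisation data for reasons that can be tied to the outcomes, and it serves no treatment purpose, because the randomised procedure is already complete. The firm quantities are the schedule losses of 16, 12, 8, 4 or 2 scores according to exit time and, if the arms have 10 patients each, a tenth of an arm per exit. Late exits cost the day 30 and day 180 BPI and satisfaction scores.

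The number of exits, and the direction and size of any bias, cannot be derived from the documents; the 0.9, 1.7 and 2.4 point shifts are illustration only. A reader might also infer that XIV excludes terminated patients from the analysis. It does not say so; it neither keeps nor excludes them. Voluntary withdrawal, and exits between randomisation and wound closure, lie outside this point. It is best treated as a cheap improvement.

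**What to change.** **XII.8.iii.** Delete it as a reason for termination and replace it with: *A condition that may affect outcome measurement is recorded with its date. Scheduled assessments and record-based outcomes continue to day 180 unless the patient withdraws consent to data collection. An assessment that cannot be done is recorded as missing with the reason.*

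**XIV.A.** Add: *All randomised patients are analysed in their allocated arm using all observed scores. A patient with some NPS scores missing has the AUC computed as the time-weighted average of the observed scores over the day 3–5 window; patients with no NPS score are reported by arm with the reason.* Express every patient's AUC on this average scale, so that complete and incomplete records are comparable.

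**XV.C.** Keep the assurance of care. Optionally add: *Receiving additional therapy does not by itself withdraw the patient from the study.*

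**Cost.** Two text changes and one optional sentence, plus the consent form if it repeats the rule. No new visits are needed, since the schedule already exists; the extra work is completing it for patients who would otherwise have left. The comparison will then include the effects of complications and added therapy. The averaging rule also assumes that a patient's missing NPS scores resemble the observed ones.
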